Primary Aim: Determine the mean change in noncalcified plaque volume in study subjects treated with high intensity statin therapy over a 24 month interval.

In addition to the 24 months follow-up period specified for the primary endpoint, we plan to follow the patients for an extended period of 12 months to study the long-term effects of the statin therapy. As a result, the patients will be followed for a total of 36 months with the first 24 months for the primary endpoint and the additional 12 months for the secondary endpoints. The secondary endpoints include:

- 1) Change in noncalcified plaque volume assessed by CCTA at the end of 36 months;
- 2) Effects of covariates including age, sex, race, body mass index and baseline plaque volume on the change of plaque volume measured by CCTA at 24 and 36 months.

- 3) (Pilot study): The relationship of CMR T1 high signal intensity plaque and change in T1 signal by CMR over time to CCTA plaque characteristics.
- 4) (Pilot study): the relationship of coronary artery plaque by CCTA to sodium fluoride (F18-NaF) uptake using positron emission tomography (PET) scanning:
 - a. Determine if F18-NaF signal correlates with CCTA defined plaque volume and CAC score.
 - b. Determine the change in F18-NaF signal in relationship to statin therapy
- a. Determine the change in F18-NaF signal in relationship to statin therapy.

BACKGROUND AND RATIONALE

CCTA is currently used to document the presence and degree of coronary artery stenosis. However, very little information is available to determine if CCTA can document *change* in the extent coronary plaque over time. Individuals who have elevated cholesterol levels are prescribed HMG-CoA reductase inhibitor ("statin") therapy; such therapy may be for the duration of an individual's life. Although the cardiovascular benefits of statin therapy have been documented in population-based studies, the benefit for an *individual* in terms of reduction of coronary artery plaque is much less well known. The use of CCTA has not been previously evaluated in this regard.

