6. STATISTICAL CONSIDERATIONS

Primary Endpoint: The primary endpoint of this study is the change in noncalcified plaque volume after 24 months.

Secondary Endpoints: In addition to the 24 months follow-up period specified for the primary endpoint, we plan to follow the patients for an extended period of 12 months to study the long term effects of the statin therapy. As a result, the patients will be followed for a total of 36 months with the first 24 months for the primary endpoint and the additional 12 months for the secondary endpoints. The secondary endpoints include:

- 1) Change in noncalcified plaque volume assessed by CCTA at the end of 36 months;
- 2) Effects of covariates including age, sex, race, body mass index and baseline plaque volume on the change of plaque volume measured by CCTA at 24 and 36 months.

- 3) The relationship of CMR T1 high signal intensity plaque and change in T1 signal by CMR over time to CCTA plaque characteristics.
- 4) (Pilot study): the relationship of coronary artery plaque by CCTA to sodium fluoride (F18-NaF) uptake using positron emission tomography (PET) scanning:
 - a. Determine if F18-NaF signal correlates with CCTA defined plaque volume and CAC score.
 - b. Determine the change in F18-NaF signal in relationship to statin therapy

Preliminary Information: One study in the literature was conducted as a pilot study with similar goals (Burgstahler et al. 2007). This pilot study investigated 22 noncalcified plaques in 12 patients before and after lipid lower therapy for 18 months. The mean patient age (61) and cardiovascular risk profile was similar to that expected in our cohort. The medication used was atorvastatin 20 mg. The mean (\pm sd) volume of all plaques was reduced by statin therapy from 0.042 ± 0.029 mL to 0.030 ± 0.014 mL ($P < 0.05$). The mean reduction of plaque volume was 0.012 mL with the standard deviation 0.017 mL.

Statistical Hypotheses: Because the study of Burgstahler et al. (2007) is based on a small sample size, we would like to consider a somewhat conservative assumption on the mean and sd for the plaque volume reduction than the preliminary information provided by this study. Specifically, we hypothesize that the patients with high intensity statin treatment will have at least 0.008 mL mean reduction of plaque volume at the end of the 24 months treatment period. Let

$$\Delta = \text{mean reduction of plaque volume at 24 months.}$$

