The statistical setting is to test the null hypothesis " $H_0: \Delta=0$ " versus the two-sided alternative of " $H_1: \Delta \neq 0$ " at 0.05 significance level with 90% power. The null hypothesis suggests that the mean plaque volume reduction is the same at the beginning of the study and the end of 24 months, while the alternative suggesting changes of the mean plaque volume at the two time points. Based on the information provided in Burgstahler et al. (2007), we believe that it is reasonable to conduct a statistical test to detect an effective Δ of at least 0.008 mL under the somewhat conservative assumption that the sd of Δ is 0.03 mL.

[figure not shown]
Sample Size Justification: We plan to conduct a group sequential trial with one interim analysis when approximately half of the patients completed the 24 months follow-up. Using the Lan-DeMets O'Brien-Fleming approximate spending function, our test requires $n=151$ patients to be followed at the end of the 24 months to reach the required 0.05 significance level and 90% power. Assuming approximately 20% dropout at the 24 month time point, the number of enrolled subjects will be 190.

Interim Analysis: The interim analysis will be conducted when $n_1=76$ patients completed the 24 months follow-up period. The lower and upper stopping boundaries for the interim analysis are $Z_1=-2.96$ and 2.96 , respectively, where Z_1 is the test statistic for the statistical hypotheses H_0 and H_1 at the interim look (see Figure 1 below). The corresponding nominal p-value at this interim look is 0.0015. The study will be considered for stopping due to efficacy if the test statistic Z_1 crosses the upper bound, i.e., $Z_1 > 2.96$, while, the study will be considered for stopping due to futility if the test statistic Z_1 crosses the lower bound, i.e. $Z_1 < -2.96$. However, the DSMB will make the decision on whether the study should be stopped at the interim look.

Final Analysis: In the most like event the study is proceeded to the final stage, the final analysis for the primary endpoint will be determined by the test statistic Z_2 with all $N=151$ patients completed the 24 months follow-up. The null hypothesis H_0 of no difference of the mean plaque volume between the baseline and the 24 months will be rejected if $|Z_2| > 1.97$ (see Figure 1 below).

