Software: Sample sizes and stopping boundaries of the group sequential design are computed using the R “gsDesign” package, version 3.1.3 (2015-03-09). Details of the statistical methods and theory of the design are described in C. Jennison and B. W. Turnbull (2000, “Group Sequential Methods with Applications to Clinical Trials”, Chapman and Hall/CRC, Boca Raton, FL).

Figure. Stopping boundaries with one interim look based on the Lan-DeMets O’Brien-Fleming approximate spending function.

Noncompliance and Missing Data: Given our past experience in similar clinical trials, we do not anticipate noncompliance as a major problem. However, despite the best possible effort, there are inevitably noncompliant patients and/or patients with missing data. We categorize the noncompliance and missing data into the following three situations:

- 1) **Noncompliant patients with complete follow-up examinations at baseline and 24 months:** The primary analysis of these patients, including both the interim analysis and the final analysis of the primary endpoint, will be carried out using the intent-to-treat (ITT) principle. Under the ITT principle, the observed plaque volumes at baseline and 24 months from these patients will be included in the primary analysis.
- 2) **Noncompliant patients with missing examinations at 24 months:** Since plaque volume normally does not decrease without significant intervention, we will apply the ITT principle to these patients using the approach of setting their plaque volumes at 24 months to be the same as their baseline values.
- 3) **Compliant patients with missing examination at 24 months:** We expect that only a small portion of the patients will fall into this category, since our study coordinators will give their best efforts to contact and keep track these patients. For the primary analysis, we will include these patients using the same approach as 2) by setting their plaque volumes at 24 months to be the same as their baseline values.

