- 4) **Secondary analysis of the above patients:** In addition to the ITT and missing data approaches mentioned in 1)-3), our secondary analysis of the primary endpoint (change of plaque volume between baseline and 36 months) will also include: a) non-ITT approach of including only treatment compliant patients in the analysis, b) complete data approach of using only patients with observed plaque volumes in both baseline and 36 months. As a sensitivity analysis, we will compare the results obtained from a) and b) above with the primary analysis of 1)-3). This sensitivity analysis will provide useful insights into the characteristics of the patients with noncompliance and/or missing plaque volume data at 24 and 36 months.

Secondary Analysis with Subgroups and Covariates: Regression models will be considered for the analysis of secondary endpoints.

- 1) **Cross-Sectional Data:** Regression models with cross-sectional outcome and covariates, i.e. data without repeated measurements over time, will include multivariable linear and nonlinear models. Nonparametric smoothing methods, such as splines and local polynomials, will be used to explore the relationships between the outcome and covariates. The flexible ANOVA F Goodness-of-Fit tests will be used to test the adequacy of the parametric linear and nonlinear regression models.
- 2) **Longitudinal Outcome and Covariate Data:** For data including repeatedly measured outcome and/or covariates over time, we will consider the commonly used linear and nonlinear mixed effects models to explore the time trends of the outcome variables and corresponding covariate effects. Similar to the exploratory analysis with cross-sectional data, we will also consider the flexible nonparametric longitudinal regression methods, such as the time-varying coefficient models and models of functional data analysis, to evaluate the appropriateness of the parametric mixed effects models.

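### The complete-case check on the 24-month primary endpoint is defined on 36-month scans, so no matching 24-month check is specified

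*Combined protocol and SAP*

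**What the plan says.** All references are to the combined protocol and SAP.

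- **Primary aim and endpoint.** Section 1 gives the aim as: "Determine the mean change in noncalcified plaque volume in study subjects treated with high intensity statin therapy over a 24 month interval". Section 6 agrees: "The primary endpoint of this study is the change in noncalcified plaque volume after 24 months".
- **36-month change.** Section 6 lists this as secondary endpoint 1: "Change in noncalcified plaque volume assessed by CCTA at the end of 36 months". Secondary endpoint 2 concerns covariate effects "on the change of plaque volume measured by CCTA at 24 and 36 months".
- **Missing-data rules for the primary analysis** (section 6, Noncompliance and Missing Data). Item 1) uses the observed volumes of noncompliant patients who have both scans. Item 2) handles noncompliant patients without a 24-month scan by "setting their plaque volumes at 24 months to be the same as their baseline values". Item 3) extends this to compliant patients without a scan: "we will include these patients using the same approach as 2"). All three rules are at 24 months.
- **Sensitivity analyses.** Item 4) reads: "our secondary analysis of the primary endpoint (change of plaque volume between baseline and 36 months) will also include" approaches a) and b). Approach a) takes treatment-compliant patients only and gives no time point. Approach b) takes only patients with a measured volume at both baseline and 36 months. Both are to be compared with the primary analysis under items 1) to 3). The closing sentence speaks of missing volumes at both 24 and 36 months.
- **Expected missingness** (section 6, Sample Size Justification): "Assuming approximately 20% dropout at the 24 month time point, the number of enrolled subjects will be 190".

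**The concern.** Item 4) attaches a 36-month time point to an endpoint that the rest of the document places at 24 months, and it does so twice. One of the two is the operative definition of the analysis set for b).

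Approach b) is the one planned analysis that would show how far the 24-month estimate depends on assigning zero change to patients without a scan. If b) is run at 36 months and set against a 24-month result, three things differ at once:

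- whether missing values are imputed;
- a further year of treatment;
- the patients included. Those scanned at 24 but not 36 months leave, and those scanned at 36 but not 24 months enter.

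Neither agreement nor disagreement between the two results could then be read as evidence about the imputation. Because two analysts could follow item 4) to different analyses, the time point might also end up being chosen after the data are seen.

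**Working it through.** **Is there a 24-month complete-case check anywhere else?**

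- *Approach a)* selects on compliance. Nothing in it removes compliant patients whose missing value item 3) sets to baseline, so it is not a complete-case analysis. Its time point can be read either way: the lead-in to item 4) points to 36 months, while the comparison with items 1) to 3) points to 24.
- *The closing sentence of item 4)* mentions both time points but defines no 24-month analysis set.
- *Secondary endpoint 2 and the mixed-effects models* in section 6 use 24-month data, but for covariate effects and time trends. Their handling of missing scans is not stated, and they are not offered as a check on items 2) and 3).

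So none is specified.

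**Inputs from section 6:** mean reduction 0.008 mL; SD of change 0.03 mL; two-sided alpha 0.05; power 90%; one interim look at about half the patients; 151 patients with 24-month follow-up; 190 enrolled.

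**The plan's own figures reproduce.**

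- Fixed design: n = (0.03 × (1.960 + 1.282) / 0.008)² = 147.8. The one-sample t version gives 149.7, so 150.
- One O'Brien-Fleming-type look at half the information gives boundaries 2.96 and 1.97. It inflates n by 148.27/147.76 = 1.0034.
- 150 × 1.0034 ≈ 150.5, so 151 as stated.
- 151/0.80 = 188.75, so 189; the plan enrols 190.

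**Effect of the imputation at 24 months.** All 190 are analysed under items 2) and 3), and completers have mean 0.008 mL and SD 0.03 mL.

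- Missing: 190 − 151 = 39; 39/190 = 0.2053. Observed fraction: 0.7947.
- Imputed mean: 0.008 × 151/190 = 0.00636 mL.
- Imputed SD: √(0.7947 × 0.03² + 0.7947 × 0.2053 × 0.008²) = 0.02694. SE: 0.02694/√190 = 0.00195.
- Complete-case mean: 0.00800 mL. SE: 0.03/√151 = 0.00244.
- Gap in means: 0.00800 − 0.00636 = 0.00164 mL, about 20% of 0.008.
- Test statistics: 0.00636/0.00195 ≈ 3.25 imputed; 0.00800/0.00244 ≈ 3.28 complete-case.

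The gap is the missing fraction times the completer mean, whatever the unobserved change in the dropouts. Over an assumed range of missingness:

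| Missing | Gap (mL) |
|---|---|
| 5% | 0.0004 |
| 20% | 0.0016 |
| 30% | 0.0024 |

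**Could a) at 24 months stand in for b)?** Let c be the share of the 39 who are compliant. Assume that a) keeps the item 3) imputation and that there are no noncompliant patients with scans. The mean is then 0.008 × 151/(151 + 39c).

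| c | Mean under a) (mL) | Difference from primary (mL) |
|---|---|---|
| 0 | 0.00800 | 0.00164 |
| 0.25 | 0.00751 | 0.00116 |
| 0.5 | 0.00709 | 0.00073 |
| 1 | 0.00636 | 0 |

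What a) reveals about the imputation therefore depends on c, which the documents do not give.

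**Size of the 36-month mismatch.** The documents give no course of plaque volume in the third year, so this cannot be estimated.

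**The case against.** The strongest reply is that this is a drafting slip whose intent can be recovered. Item 4) names the primary endpoint, is compared with the 24-month analysis, and ends by mentioning both time points. That is plausible, but the text does not settle whether 36 is an error for 24 or whether item 4) was meant for secondary endpoint 1. Either way it needs correcting.

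Second, the Final Analysis paragraph of section 6 describes the final test statistic as based on the 151 patients who completed 24 months, which reads like a completer analysis. It is presented as the primary test, however, not as a check on the imputation. It also sits uneasily with items 2) and 3), which add imputed patients. It does not fill the gap.

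Third, the practical stake is modest. The test statistic hardly changes, and a reader who knows the number missing can recover the complete-case mean by dividing the imputed mean by the observed fraction. Nor can a complete-case analysis show that the imputation is right. All of this stands. But the primary aim is to determine a mean change, so a shift of about 20% in the estimate matters even when the test does not move. The comparison that the plan does prescribe would still be uninterpretable.

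Fourth, item 3) expects few compliant patients without scans. That favours low values of c, where a) at 24 months would come close to the complete-case result. This is fair as to the numbers, but it depends on a) being run at 24 months, which the plan does not say.

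**Conclusion.** The concern holds. Item 4) contradicts the endpoint definition and, followed literally, leaves the 24-month primary analysis without a complete-case sensitivity analysis. For a) the time point is ambiguous rather than absent.

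At the planned missingness, the undisplayed dependence on imputation is about 0.0016 mL on a completer mean of 0.008 mL. This rests on the plan's mean and SD applying to completers and on all 190 enrolled being analysed. Only the 20% dropout comes from the documents; the 5% and 30% figures are assumptions.

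What is at stake is a usable, prespecified supporting analysis. It should be fixed, but it does not threaten the main test.

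**What to change.** In section 6, Noncompliance and Missing Data, item 4):

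1. Change 36 months to 24 months in the parenthesis that describes the primary endpoint and in the definition of approach b), so that a) and b) are both run at 24 months and compared with items 1) to 3).
2. State that b) shows sensitivity to the baseline-value imputation without proving it right or wrong, and that a) shows sensitivity to noncompliance.
3. Say whether a) keeps imputed values for compliant patients without a 24-month scan.
4. If 36-month versions are wanted, list them separately under secondary endpoint 1, compare them with a 36-month analysis, and state the missing-data rule for that analysis. The present rules cover 24 months only.

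The cost is a wording change in two places plus a few clarifying sentences. No new data are needed, because CT angiography at 24 months is already in the study calendar (Appendix A).

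### No planned analysis tests the zero-change value given to patients without a 24-month scan; read at 24 months, the completer comparison in item 4) cannot do so

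*Combined protocol and SAP*

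**What the plan says.** All of this is in section 6, under Noncompliance and Missing Data.

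- Items 2) and 3) handle missing 24-month scans in the same way for noncompliant and compliant patients, by "setting their plaque volumes at 24 months to be the same as their baseline values". Each such patient enters the primary analysis with a change of zero.
- Item 4) adds two analyses. Approach a) keeps only treatment-compliant patients. Approach b) is a "complete data approach of using only patients with observed plaque volumes in both baseline and 36 months".
- Item 4) then compares a) and b) with the primary analysis as the sensitivity analysis and concludes: "This sensitivity analysis will provide useful insights into the characteristics of the patients with noncompliance and/or missing plaque volume data".

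Item 4) describes the primary endpoint as change to 36 months. The Design section and the opening of section 6 define it at 24 months.

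No delta-adjusted, tipping-point or imputation analysis appears. Mixed-effects models are named for secondary endpoints only. The 12-month CCTA is scheduled for everyone in follow-up (Appendix A), but it has no role in the missing-data handling.

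**The concern.** A sensitivity analysis for missing data should change the assumption about the missing patients and show whether the conclusion moves. Here the primary analysis enters them as zeros and a complete-data analysis at the same month leaves them out. Neither uses their outcomes, their 12-month scans or their baseline covariates, so the contrast cannot say anything about them.

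This matters because the trial has one arm, the estimand is a mean change, and the plan itself allows for about one patient in five having no 24-month scan. Under section 3.4.1, patients who come off treatment return to usual care and are imaged only if they consent. Loss of the scan could therefore be linked to stopping the statin. If so, similar results from the two analyses could be mistaken for evidence that dropout did no harm.

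**Working it through.** **Inputs, all from section 6.** The test of no mean change is two-sided "at 0.05 significance level with 90% power"; it is designed "to detect an effective Δ of at least 0.008 mL", and it assumes that "the sd of Δ is 0.03 mL". The final bound is 1.97. There are 151 patients with 24-month data and 190 enrolled, so 39 are missing. I take the filled analysis to contain all 190, as items 2) and 3) imply, and consider the final look only.

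**The plan's own figure.** Fixed-sample n = (0.03 × (1.960 + 1.282) / 0.008)² = 147.8 by the normal formula, or 150 by the t-test. The Lan-DeMets O'Brien-Fleming function with one look at half the information gives bounds of 2.963 and 1.969 and an inflation factor of 1.0034. Then 150 × 1.0034 = 150.5, rounded up to 151, as stated. Dropout: 151 / 0.8 = 189, against 190 stated. The design reproduces.

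**Zero fill against completers, both at 24 months.** Let S be the sum of the observed changes and Q the sum of their squares. For a one-sample t on n patients,

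t² / (t² + n − 1) = S² / (nQ).

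Adding zeros leaves S and Q alone and replaces n = 151 by N = 190. Hence:

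- filled mean / completer mean = 151/190 = 0.795, always;
- t_filled² / (t_filled² + 189) = (151/190) × t_comp² / (t_comp² + 150).

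For t_comp = 1.970: 3.881/153.881 = 0.02522; × 0.795 = 0.02004; t_filled² = 189 × 0.02004 / 0.97996 = 3.866; t_filled = 1.966. In the same way 3.266 becomes 3.245. Solving backwards, t_filled = 1.970 needs t_comp = 1.974. The decisions differ only when the completer |t| lies between 1.970 and 1.974. With noncentral t probabilities:

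| Completer mean reduction (mL) | Same decision |
|---|---|
| 0 | 99.96% |
| 0.004 | 99.85% |
| 0.005 | 99.85% |
| 0.008 | 99.93% |

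At 0.008 mL each test rejects in about 90.3% of trials. No quantity here depends on the missing patients' outcomes.

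**Approach b) as written, at 36 months.** The documents give no 24/36-month correlation or later loss. I assumed correlations of 0.5 to 0.9, equal means, SD 0.03 mL and 10 further losses. Simulated agreement with the primary test is about 86-92% at 0.008 mL and 68-84% at 0.004 mL. The added disagreement comes from a different month and a different set of patients.

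**Approach a).** I assumed that 8 to 30 scanned noncompliers are removed, with mean changes from a 0.008 mL reduction to a 0.008 mL increase. Agreement at 0.008 mL is then about 65-96%.

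**Scenario for the untested value.** Completers: mean reduction 0.008 mL, SD 0.03 mL. Give the 39 missing patients a mean reduction m with the same SD:

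- overall mean = (151 × 0.008 + 39m)/190;
- variance = 0.03² + 0.795 × 0.205 × (0.008 − m)²;
- Z = mean / √(variance/190).

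| m (mL; negative is growth) | Overall mean (mL) | Z, all 190 |
|---|---|---|
| +0.008 | 0.0080 | 3.68 |
| 0 | 0.0064 | 2.90 |
| −0.008 | 0.0047 | 2.12 |
| −0.0095 | 0.0044 | 1.97 |
| −0.017 | 0.0029 | 1.25 |

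The full-data result tips at growth of about 0.0095 mL. On an assumed baseline of 0.042 mL (the mean in the pilot study cited in section 6) that is 0.0095 / (2 × 0.042), about 11% per year.

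**The case against.** A reader might infer that the planned sensitivity analysis would agree with the primary test about 99.9% of the time whatever happened to the missing patients, and that it uses no data on them. The documents do not support that, for four reasons.

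- **Item 4) b) is written at 36 months.** The 99.9% figure needs the 24-month reading. A patient who missed month 24 but was scanned at month 36 enters b) with a real measurement. As an illustration, suppose 10 of the 39 return at month 36, with a 24/36-month correlation of 0.7. Agreement is then 89% if they regressed by 0.008 mL and 77% if they grew by 0.0168 mL. This stands. The comparison still cannot separate the effect of missing 24-month data from the change of month.
- **Approach a) is part of the comparison** and can differ materially from the primary test. This also stands. Its information is about noncompliers who were scanned; it does not test the value assigned to unscanned patients.
- **The plan compares results, not only decisions,** and the two 24-month means differ by about 20%. That is true, but the gap is the missing fraction itself, 39/190.
- **Mixed-effects models are planned** and could use 12-month scans. They are tied to secondary endpoints, are partly exploratory, and do not vary the assumed change.

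A reader might also infer that dropout would in fact overturn the result. The documents do not show that. The 9-20% yearly growth in Table 2 is natural-history or placebo data, whereas Table 3, during therapy, runs from −25% to +18% per year. The 0.042 mL figure averages 22 plaques in 12 patients, while this trial measures each patient's largest noncalcified plaque.

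**Conclusion.** The point holds in a limited form. No planned analysis tests the zero-change assumption for the roughly 20% of patients expected to lack a 24-month scan. With b) read at 24 months, 151 observed and 39 missing, the comparison with the primary analysis is fixed by algebra: a mean ratio of 0.795 and the same decision in about 99.85% to 99.96% of trials for completer means of 0 to 0.008 mL. Correcting 36 to 24 months in item 4), with no other change, would therefore leave a nearly redundant check. As written at 36 months the results can differ more, but the cause of a difference cannot be identified. The claim of insight into patients with missing plaque volumes is not supported for those missing at 24 months; for scanned noncompliers, a) does give information.

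The tipping value of about 0.0095 mL growth is a scenario. It rests on the design mean and SD and on all 39 missing patients sharing one mean change. It shows that the untested value can matter, not that it will. The 36-month and compliant-only agreement ranges rest on assumed correlations, losses and numbers of noncompliers that the documents do not give.

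**What to change.** Keep the primary analysis, and keep a) as a compliance analysis. In item 4):

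1. State the sensitivity analysis of the primary endpoint at 24 months.
2. Compare patients with and without a 24-month scan on baseline covariates, baseline plaque volume and baseline-to-12-month change.
3. Add a delta-adjusted (tipping-point) analysis at 24 months. Impute the missing changes with proper residual variance, using the 12-month scan where there is one. Vary the missing patients' mean change, for example from a 0.008 mL reduction to a 0.017 mL increase (the upper end is 20% per year for two years on 0.042 mL). Report where |Z2| falls below 1.97.
4. Delete the sentence on insight into patients with missing data, or limit it to what a) and step 2 can show.

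The cost is SAP wording and a little more analysis, with no new visits, scans or patients. The downside is that a significant primary result may be shown to be fragile to dropout.
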